8.7.5 Missed Doses During Up-Dosing and Maintenance

Missed doses of study product can pose a significant risk to subjects anytime during the study, and the greatest risk is considered to be during up-dosing. Procedures for missed consecutive doses of study product during up-dosing and maintenance are described in [Table 16](#).

Table 16: Procedures for Missed Consecutive Doses of Study Product

Missed Doses [1]	Action
1-2 consecutive doses	Resume next dose at current dose level at home or at the study site.
3-4 consecutive doses	Resume next dose at current dose level under medical supervision at the study site, or at approximately 50% (rounded down to the nearest feasible whole dose) at home at investigator discretion.
≥ 3 consecutive doses on 3 occasions	Stop study product dosing and discontinue the subject early from the study (Section 5.3), unless the dose was withheld for an adverse event or study product dispensing error.
5-7 consecutive doses	Reinitiate next dose at approximately 50%-70% (rounded down to the nearest feasible whole dose) of last tolerated dose under medical supervision at the study site at investigator discretion. 
 • If dose is tolerated, resume dose escalation with 1 dose level increase every 1-4 weeks until the dose returns to the last tolerated dose level. • If symptoms occur, follow the dose adjustment guidelines (Section 8.7.3.2).
> 7 consecutive doses due to noncompliance	Stop study product dosing and discontinue the subject early from the study (Section 5.3), unless the dose was withheld for management of intercurrent illness, or for an adverse event or study product dispensing error.
8-14 consecutive doses (due to adverse event or study product dispensing error)	Reinitiate dosing under medical supervision at the study site as follows: 
 • If the missed doses occurred at a dose level of ≤ 120 mg, reinitiate next dose at approximately 25% (rounded down to the nearest feasible whole dose) of last tolerated dose. • If the missed doses occurred at a dose level of ≥ 160 mg, dosing may be reinitiated at the nearest whole dose that is approximately 25%-50% of the last tolerated dose, at the discretion of the investigator. • If the pause in dosing was during maintenance, dosing may be reinitiated at the nearest whole dose that is approximately 50% of the last tolerated dose, at the discretion of the investigator. • If tolerated, resume dose escalation with 1 dose level increase every 1-4 weeks until the dose returns to the last tolerated dose level. • If symptoms occur, follow the dose adjustment guidelines (Section 8.7.3.2).
≥ 15 consecutive days	Stop study product dosing and discontinue the subject early from the study (Section 5.3).

[1] For missed doses at the 1 mg dose level, reinitiate next dose at 1 mg at home or at the study site depending on the duration of missed doses.

8.7.6 Adverse Events of Interest

Adverse events of interest include systemic allergic reactions assessed as grade 2 or higher (including anaphylaxis), GI adverse events with prolonged dose interruption (> 7 consecutive days) or that result in early discontinuation, accidental and nonaccidental food allergen exposure, adverse events with severe symptoms, and use of epinephrine. These events require rapid reporting as described in [Section 8.8.2](#).

Allergic reactions during food challenges will not be considered related to study product or reported as adverse events of interest.

8.7.6.1 Systemic Allergic Reactions Assessed as Grade 2 or Higher, Including Anaphylaxis

The protocol criteria for systemic allergic reaction are provided in [Table 7](#). The assessment of anaphylaxis is described in detail in [Section 8.4.1](#). Adverse events of systemic allergic reaction assessed as grade 2 or higher per the systemic allergic reaction grading system ([Section 8.6](#)), including anaphylaxis (ie, grade ≥ 3 per the systemic allergic reaction severity grading system [[Table 9](#)]) and meets the protocol-specified criteria for anaphylaxis [[Table 8](#)]), are considered adverse events of interest and require rapid reporting as described in [Section 8.8.2](#).

8.7.6.2 GI Adverse Events

For chronic or recurrent GI symptoms, especially upper GI symptoms, investigators are advised to consider dose reduction of study product or early discontinuation as appropriate due to the potential for EoE. EoE presents with varied symptoms of esophageal dysfunction that differ between children and adults ([Dellon, 2013](#); [Dellon, 2011](#)). In children, the symptoms are often nonspecific and may include feeding difficulties, failure to thrive, abdominal pain, regurgitation, nausea, and vomiting. In adults, the most frequent symptoms are dysphagia and food impaction; less frequent symptoms include heartburn, chest pain, abdominal pain, nausea, or vomiting. Special attention should be paid to these symptoms, which may suggest esophageal dysfunction, particularly when the symptoms are new in onset during the study, chronic or recurrent, or experienced as a complex of multiple symptoms.

Investigators are encouraged to request consultation from an outside physician or conduct additional testing to assist in the diagnosis or management of chronic or recurrent GI adverse events at their discretion. If a subject is seen by a gastroenterologist, study site personnel must obtain the records for the visit and the test results, including those from endoscopy and endoscopic biopsy if performed, and retain them in the subject's source documents.

If GI symptoms develop that suggest a chronic or recurrent reaction to study product, the dose level should be reduced ([Table 13](#)). The level of the dose reduction should be guided by the severity of the symptoms. Symptomatic treatment is permitted ([Section 7.2](#)) but should be used to supplement dose reduction and not as a substitute for it.

8.7.6.2.1 GI Adverse Events of Interest

GI adverse events of interest are as follows:

- GI adverse events leading to prolonged dose interruption, defined as withholding study product for > 7 consecutive days due to GI adverse events anytime during the study
- GI adverse events that result in early discontinuation

GI adverse events of interest require rapid reporting as described in [Section 8.8.2](#). Subjects aged ≥ 8 years and parents/caregivers of subjects aged 4 to 18 years will be asked to

complete the PEESS v2.0 questionnaire while the subject is symptomatic and thereafter at intervals as described in [Section 5.5.1](#). Additional information about the PEESS v2.0 questionnaire is provided in [Section 9.3.4](#).

After early discontinuation or study exit, subjects who had GI adverse events of interest will have safety follow-up as described in [Section 5.5.1](#). Safety follow-up procedures are provided in [Appendix 6](#).

8.7.6.3 Accidental and Nonaccidental Food Allergen Exposure

Accidental food allergen exposure is any known or suspected exposure to a food to which the subject is allergic, including egg, whether or not the exposure results in an adverse event. Nonaccidental food allergen exposure is any intentional exposure to a food to which the subject is allergic, including egg, whether or not the exposure results in an adverse event. Accidental and nonaccidental food allergen exposure are considered adverse events of interest and require rapid reporting as described in [Section 8.8.2](#).

Subjects and parents/caregivers will be asked to contact the study site after subjects have any food allergen exposure, even if it does not result in symptoms. The subject may be asked to return to the study site.

8.7.6.4 Severe Adverse Events

Adverse events assessed by investigators as severe by either of the 2 severity grading systems (systemic allergic reaction grading system or general adverse events grading system, [Section 8.6](#)) are considered adverse events of interest and require rapid reporting as described in [Section 8.8.2](#). Severe allergy symptoms will result in early discontinuation during initial dose-escalation days 1 and 2 ([Table 12](#)) and may result in early discontinuation during up-dosing and maintenance ([Table 13](#)).

8.7.6.5 Adverse Events Requiring Use of Epinephrine

Adverse events, especially allergic reactions, may result in epinephrine use, as described in [Section 8.7.2](#). Adverse events requiring use of epinephrine are considered adverse events of interest and require rapid reporting as described in [Section 8.8.2](#).

8.7.7 Other Notable Events

Other notable events include overdose and pregnancy.

8.7.7.1 Overdose

An overdose is defined as any dose of study product greater than the prescribed dose within 1 calendar day. The medical monitor must be contacted as soon as possible in the event of a study product overdose. The subject is to be monitored closely for any adverse events and

treated for symptoms. The amount of the overdose and its duration are to be recorded in the subject's source documents.

8.7.7.2 Pregnancy and Other Reproductive Considerations

Egg OIT may increase the risk of allergic reactions, including anaphylaxis. Anaphylaxis can cause a dangerous decrease in blood pressure, which could result in compromised placental perfusion and significant risk to a fetus during pregnancy. In addition, the effect of egg OIT on the immune system of the mother and fetus during pregnancy is unknown. Therefore, all female subjects of childbearing potential must have a negative serum pregnancy test before the first dose of study product and a negative urine test during the treatment period and must avoid pregnancy during the study.

All postmenarchal female subjects will be provided with age-appropriate counseling and information about contraception per the standard of care at the study site. The information should include adequate information about the use, effectiveness, and side-effects of contraceptive methods, and be conducted in as private a setting as possible using a sensitive, patient-centered approach. Sexually active females of childbearing potential will be required to use one of the following types of contraception:

- A highly effective method of birth control, defined as one that results in a low failure rate (ie, < 1% per year) when used consistently and correctly, as follows:
 - Combined (estrogen- and progestogen-containing) hormonal contraception associated with inhibition of ovulation (oral, intravaginal, or transdermal).
 - Progestogen-only hormonal contraception associated with inhibition of ovulation (oral, injectable, or implantable).
 - Intrauterine device.
 - Intrauterine hormone-releasing system.
 - Bilateral tubal occlusion.
 - Vasectomized partner.
 - Sexual abstinence.
- If a highly effective single method of birth control is not used, an effective, double-barrier method of contraception should be used (eg, male condom in conjunction with a cervical cap, diaphragm, or contraceptive sponge with spermicide).

Females of childbearing potential are defined as all women physiologically capable of becoming pregnant, including women whose career, lifestyle, or sexual orientation precludes intercourse with a male partner and women whose partners have been sterilized by vasectomy or other means, unless they meet the following criteria: at least 12 months of natural (spontaneous) amenorrhea, 6 months of spontaneous amenorrhea with serum follicle stimulating hormone levels > 40 IU/L, or at least 6 weeks after surgical bilateral oophorectomy with or without hysterectomy or hysterectomy.

8.8 Adverse Event Reporting

Safety reporting to regulatory authorities will be implemented according to global and country-specific regulations.

To elicit adverse event reports, the study site personnel should question the subject and parent/caregiver in a general way without suggesting specific symptoms. Adverse events may be identified during study visits, subject or parent/caregiver contact with the study site, or during the review of the subject's diary.

[figure not shown]
All signs and symptoms associated with an adverse event, whether or not related to the study product, must be fully and completely documented **for all subjects** (ie, both treatment groups) on the adverse event case report form and in the subject's source documents. In addition, any adverse event resulting in permanent treatment discontinuation must be recorded on the appropriate case report form, as well as documented in the subject's source documents.

Adverse event terms should include a diagnosis, as available, and is preferred to listing all the individual signs and symptoms. If the diagnosis is not known, the investigator is to record each sign and symptom as an individual adverse event. For multiple symptoms of allergic reactions/hypersensitivity, each individual symptom is to be entered separately on the case report forms.

8.8.1 Adverse Event Reporting Period

Collection and reporting of adverse event information will begin at the time the screening informed consent/assent form is signed and will continue for all subjects through 14 days after the last dose of study product, or through study exit for subjects receiving AR201 treatment in a follow-on study ([Figure 4](#)).

Figure 4: Adverse Event Reporting Period

[1] Subjects with unresolved adverse events at early discontinuation or study exit, or gastrointestinal adverse events of interest will have safety follow-up.

All adverse events from the start of study treatment must be documented on the adverse event case report form and in the subject's source documents. Any event occurring during

screening and before the first dose must also be documented on the appropriate case report form and in the subject's source documents.

8.8.2 Reporting for Serious Adverse Events, Adverse Events of Interest, and Other Notable Events

Serious adverse events and adverse events of interest for **all subjects** (ie, both treatment groups) require rapid reporting **within 24 hours** of the study site personnel's knowledge of the event, regardless of the investigator assessment of the relationship of the event to study product.

The initial report should include, at minimum, the following:

- Study number (AIME01)
- Site name and number
- Investigator name
- Subject ID number, sex, and age (unless omitted per local regulations)
- Details of study treatment
- The date of the report
- A description of the event (event term, severity)

Initial reporting should not be delayed, and additional follow-up reports may be submitted as new information becomes available. Follow-up reports should include date of onset, study site/hospital records, discharge summary, resolution date, treatment and action for the event, assessment of relatedness to study product, and any other applicable information.

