Up-dosing will be approximately 6 months (22-40 weeks), with dose escalation occurring approximately every 2 weeks. Daily doses of study product during up-dosing will be 1, 3, 6, 12, 20, 40, 80, 120, 160, 200, 240, and 300 mg/day. The first dose of study product at each new dose level will be administered under medical supervision at the study site; the remaining doses at each dose level will be administered daily at home as tolerated. Dose adjustments may be allowed. Subjects who reach the 300 mg/day dose within 40 weeks and tolerate the first 300 mg dose with no more than mild symptoms that are not dose-limiting will begin the maintenance period. Subjects who do not reach the 300 mg/day dose within 40 weeks of day 1 will discontinue early from the study.

Subjects who begin maintenance treatment will continue daily dosing with study product at 300 mg/day for approximately 12 weeks, which may be extended by up to an additional 4 weeks to accommodate dose adjustments during the last 2 weeks of maintenance. Study site visits will occur approximately every 4 weeks. Study product will be administered under medical supervision at the study site during maintenance visits; subsequent maintenance doses will be administered daily at home as tolerated. At the end of maintenance, subjects will have an exit DBPCFC up to a single highest challenge dose of 2000 mg dried egg white protein (4043 mg cumulative) or placebo, followed by an open baked whole egg food challenge within 14 days after the second day of the exit DBPCFC. Subjects must tolerate the 300 mg daily dose of study product for approximately 2 consecutive weeks before having the exit DBPCFC.

Subjects who complete the exit DBPCFC and attempt the open baked whole egg food challenge will exit (complete) the study. Study treatment assignment will be unblinded for a subject after study exit and after all major data queries for the subject are resolved. For a subject who discontinues early from the study, study treatment assignment will be unblinded after the study is completed. Eligible subjects will have the option to enroll in an open-label, follow-on study to receive AR201 treatment until it becomes commercially available or product development is terminated.

At early discontinuation or study exit, subjects with unresolved adverse events or who had gastrointestinal (GI) adverse events of interest (ie, GI adverse events that result in dose

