5.4 Study Exit

Study exit procedures are listed in [Appendix 5](#).

Completion of study exit procedures, including both days of the exit DBPCFC and attempting the open baked whole egg food challenge, will be considered as completing the study. Eligible subjects will have the option to enroll in an open-label, follow-on study to receive AR201 treatment until it becomes commercially available or product development is terminated. Blinded study treatment may continue in this study if the follow-on study is not yet available at the study site when subjects complete their course of treatment. The treatment assignment for each subject will be unblinded after study exit, after all major data

queries for the subject are resolved, and the open-label follow-on study is available at the study site.

Subjects with unresolved adverse events at study exit or who had GI adverse events of interest (ie, GI adverse events that result in dose interruption > 7 consecutive days or early discontinuation; [Section 8.7.6.2.1](#)) will have safety follow-up per [Section 5.5](#).

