10.6 Analysis of Safety

All safety analyses will be performed using the safety population. Safety data will be summarized and listed by treatment received.

Safety data will be collected from signed informed consent and assent (where required) through 14 days after the last dose of study product, or through study exit for subjects receiving AR201 treatment in a follow-on study.

Adverse events will be classified by system organ class and coded to preferred term using the Medical Dictionary for Regulatory Activities (MedDRA). Adverse events will be classified by severity using the systemic allergic reaction grading system for systemic allergic reactions including anaphylaxis, and the general adverse events grading system for all other adverse events ([Section 8.6](#)). Anaphylaxis is defined as a severe, potentially life-threatening systemic allergic reaction (ie, grade ≥ 3 per the systemic allergic reaction grading system [[Section 8.6](#)]) that meets the criteria for anaphylaxis per [Section 8.4.1](#).

Summaries of the safety of AR201 and placebo treatment during the study will include the following:

- Overall summary of adverse events
- Incidence of all nonserious and serious adverse events
- Incidence of adverse events by severity grade
- Incidence and severity of treatment-related adverse events
- Incidence of dose modifications
- Exposure-adjusted event rates for the most frequent adverse events (ie, adverse events in $\geq 5\%$ of the safety population)
- Exposure-adjusted event rates for the most frequent treatment-related adverse events (ie, adverse events in $\geq 5\%$ of the safety population)
- Incidence of early treatment discontinuation due to adverse events and due to chronic or recurrent GI adverse events
- Separate summaries will be presented for adverse events considered allergic reactions, systemic allergic reactions, use of epinephrine, and accidental/nonaccidental food allergen exposure

Adverse events with onset before the first dose of study treatment will be listed only.

All medications will be coded using the World Health Organization Drug Dictionary (WHO-DD). Medications will be listed and summarized by Anatomical Therapeutic Chemical (ATC) classification system level 1 and preferred name.

- Prior and concomitant medications, excluding rescue medications, will be summarized separately by ATC class, preferred name, and treatment.

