- [4] Early discontinuation: For subject who discontinues treatment early; approximately 14 days after the last dose.
Exit: For subject who completes the exit DBPCFC and open baked whole egg food challenge.
- [5] Complete before the exit DBPCFC begins (on the first day only) and after the open baked whole egg food challenge.
- [6] For subject aged ≥ 6 years, obtain PEF at approximately the same time of day for each assessment visit (eg, morning, afternoon); record the best result of 3 attempts. Obtain spirometry if PEF shows a clinically relevant reduction, subject has clinical deterioration (eg, active wheeze on physical examination), or as clinically indicated at unscheduled visits; record the best result of 3 attempts (if unable to successfully obtain, record attempts and investigator assessment).
For subject aged 4-5 years, obtain PEF; record results (if unable to successfully obtain, record attempts and investigator assessment).
- [7] Symptom-directed: Assess systems per standard of care at the study site or as clinically indicated by symptoms.
Complete: Assess systems (eg, general appearance, head, eyes, ears, nose, mouth, skin, heart, lungs, lymph nodes, gastrointestinal, genitourinary, neurologic, and skeletal).
- [8] Instruct subject to avoid eating raw or undercooked hen eggs or food known to contain raw or undercooked hen eggs during the study. Provide food/egg allergy education (including recognition of an allergic reaction, administration of epinephrine auto-injector, anaphylaxis action plan, ways to minimize accidental exposure to egg) per standard of care at the study site. Instruct subject who tolerates the screening open baked whole egg food challenge without dose-limiting allergy symptoms to include baked egg in their diet per Mount Sinai baked egg guidelines. Instruct subject who has dose-limiting symptoms during the open baked whole egg food challenge to avoid all forms of hen egg during the study.
- [9] Include review of symptoms recorded in subject diary. For subject with GI adverse events of interest, instruct subject aged ≥ 8 years and parent/caregiver of subject aged 4-18 years to complete the PEESS v2.0 questionnaire while the subject is symptomatic, at early discontinuation or study exit, and during safety follow-up. Subject with unresolved adverse events at early discontinuation or exit and subject with GI adverse events of interest will have safety follow-up per [Appendix 6](#).

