- [10] Review medications since previous visit. Instruct subject to discontinue antihistamines and other medications that could interfere with the assessment of an allergic reaction 5 half-lives of the medication before initial dose-escalation day 1, skin prick tests, the exit DBPCFC, and exit open baked whole egg food challenge. Review the prescribing information to determine the half-life of each medication for the subject's relevant age group.

- [11] Administer study product at the study site per the dose modification guidelines. Measure blood pressure and heart rate and assess signs/symptoms of allergic reaction at 15-30 minutes postdose and approximately every 30 minutes thereafter (until 90 minutes postdose or end of observations for symptoms, whichever is last).
- [12] Review instructions for administration of study product at home. Instruct that subject withhold study product when it will be administered at the study site and on the days of the exit DBPCFC and open baked whole egg food challenge.
- [13] Contact subject or parent/caregiver by telephone on the day after initial dose-escalation day 2, up-dosing visits, maintenance visits, exit DBPCFC, and open baked whole egg food challenge for adverse events review and to inquire about compliance with study product dosing. Remind the subject or parent/caregiver to record symptoms in the diary (except after the exit open baked whole egg food challenge).
- [14] Perform/collect before the exit DBPCFC (on the first day only).
- [15] Subject must tolerate the 300 mg daily dose for approximately 2 consecutive weeks before having the exit DBPCFC. Conduct on 2 separate days within 7 days.
- [16] Conduct within 14 days after the second day of the exit DBPCFC. If circumstances create a safety risk (eg, an intercurrent illness), the open baked whole egg food challenge may be delayed after discussion with the medical monitor.
- [17] Refer to the laboratory manual for sample collection and processing.
- [18] Complete blood count with differential. Total IgE, egg white-specific and egg white component IgE, and egg white-specific IgG4.
- [19] For all females of childbearing potential.

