ACT, Asthma Control Test; C-ACT, Childhood Asthma Control Test; DBPCFC, double-blind, placebo-controlled food challenge; EASI, Eczema Area and Severity Index; ED, early discontinuation; Esc, escalation; FAIM, Food Allergy Independent Measure; FAQLQ, Food Allergy Quality of Life Questionnaire; GI, gastrointestinal; Ig, immunoglobulin; na, not applicable; opt, optional; PEESS v2.0, Pediatric Eosinophilic Esophagitis Symptom Scores version 2; PEF, peak expiratory flow; q, every; TNSS, Total Nasal Symptom Score; Unsch, unscheduled; w, weeks.

Appendix 6: Study Schedule of Activities for Subjects Who Discontinue Treatment Early, Exit With Ongoing Adverse Event, or Have Gastrointestinal Adverse Events of Interest: Safety Follow-Up

Activity	Ongoing Adverse Events at Early Disc / Exit [1]	GI Adverse Events of Interest	
		Dose Interruption > 7 Consecutive Days Due to GI AEs	Early Disc Due to GI AEs [2]
Adverse events review [3]	X		X
Concomitant medications review			X
Symptom-directed physical examination [4]			X
PEESS v2.0 questionnaire [5]		X	X

- [1] Safety follow-up for ongoing adverse events is for 30 days or until consent for follow-up is withdrawn. Safety follow-up for ongoing serious adverse events is for 30 days or until the ongoing serious adverse events resolve or stabilize, whichever is last, or until consent for follow-up is withdrawn.
- [2] Safety follow-up at the study site (or by telephone if appropriate; includes review of medical records and procedure results from specialist visits [eg, endoscopy results, pathology results], if applicable) is monthly for the duration of safety follow-up ([Section 5.5.1](#)).
- [3] For adverse events ongoing at early discontinuation or study exit. Telephone subject or parent/caregiver for subject who does not come to the study site.
- [4] Assess systems per standard of care at the study site or as clinically indicated by symptoms.
Telephone follow-up by medically qualified personnel may be appropriate in the absence of symptoms, at the discretion of the investigator.
- [5] Instruct subject aged \geq 8 years and parent/caregiver of subject aged 4-18 years to complete the questionnaire at early discontinuation or study exit and monthly for the duration of safety follow-up ([Section 5.5.1](#)).

AE, adverse event; Early Disc, early discontinuation; GI, gastrointestinal; PEESS v2.0, Pediatric Eosinophilic Esophagitis Symptom Scores version 2.0.

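### Completers who do not enter the follow-on study have no scheduled contact at the end of the 14-day adverse event window

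*Protocol*

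**What the plan says.** **The window.** Section 8.8.1 states that collection "will continue for all subjects through 14 days after the last dose of study product". The same sentence then makes its single exception, worded as "or through study exit for subjects receiving AR201 treatment in a follow-on study". Section 10.6 gives the same period for the safety analysis: "through 14 days after the last dose of study product, or through study exit for subjects receiving AR201 treatment in a follow-on study". The Synopsis agrees.

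**Who the exception leaves out.** Section 5.4 makes the follow-on study optional and conditional: "Eligible subjects will have the option to enroll in an open-label, follow-on study". The protocol therefore allows for completers who owe the full 14 days.

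**The schedule.** Appendix 5, note 4, times one of the two final visits: "Early discontinuation: For subject who discontinues treatment early; approximately 14 days after the last dose". Section 5.3 says the same. The other visit, Exit, is tied to finishing the challenges and has no timing relative to the last dose. Section 3.1 defines that point: "Subjects who complete the exit DBPCFC and attempt the open baked whole egg food challenge will exit (complete) the study". Appendix 5, note 13, lists the calls: "Contact subject or parent/caregiver by telephone on the day after initial dose-escalation day 2, up-dosing visits, maintenance visits, exit DBPCFC" and the exit baked egg challenge. It drops the diary reminder after that last challenge.

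**Later follow-up.** Section 5.5 and Appendix 6 provide follow-up for subjects with events unresolved at exit or with gastrointestinal events of interest. Appendix 6, note 3, restricts the adverse event review: "For adverse events ongoing at early discontinuation or study exit".

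**The concern.** The protocol states one collection period for every subject outside the follow-on study, but the schedule supplies an end-of-period assessment to only one of the two disposition groups. An early discontinuer is actively questioned at about day 14. A completer who does not roll over is last questioned the day after the baked egg challenge, whatever the interval since the last dose.

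Safety and tolerability is a secondary objective, and Section 1.2 describes this as a first-in-human study of the product. A table of events through 14 days after the last dose would combine subjects who were asked over the whole window with subjects who were asked over part of it. Sites also cannot deliver Section 8.8.1 uniformly from Appendix 5, because the contact it needs is not on the schedule.

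**Working it through.** **Inputs**

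- Required window: 14 days after the last dose (Sections 8.8.1 and 10.6).
- Exit DBPCFC: two separate days within 7 days (Appendix 5, note 15). Let g be the days from challenge day 1 to challenge day 2, taken as 1 to 7.
- Baked egg challenge: within 14 days after DBPCFC day 2 (note 16). Let b be that interval, 1 to 14.
- Last scheduled contact: the call one day after the baked egg challenge (note 13; Appendix 2, post-challenge instruction 7).
- Study product is withheld on the days of the exit challenges (note 12). The protocol gives no last-dose date for completers.

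Call DBPCFC day 1 day 0. DBPCFC day 2 is then day g, the baked egg challenge is day g + b, and the last call is day g + b + 1. There are 7 × 14 = 98 permitted schedules.

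**Reading A: dosing continues on non-challenge days, as note 12 implies**

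- b of 2 or more: last dose on day g + b − 1. Interval to the last call = (g + b + 1) − (g + b − 1) = 2 days. This covers 7 × 13 = 91 schedules.
- b = 1 and g of 2 or more: last dose on day g − 1. Interval = (g + 2) − (g − 1) = 3 days. This covers 6 schedules.
- b = 1 and g = 1: last dose on day −1. Interval = 3 − (−1) = 4 days. This covers 1 schedule.

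The last contact falls 2 to 4 days after the last dose and reaches day 14 in none of the 98 schedules. The days without scheduled assessment number 14 − 4 = 10 to 14 − 2 = 12.

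**Reading B: dosing ends the day before DBPCFC day 1**

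The last dose is on day −1, so the interval is (g + b + 1) − (−1) = g + b + 2. It runs from 1 + 1 + 2 = 4 to 7 + 14 + 2 = 23 days. It is short of day 14 when g + b is 11 or less. For g = 1 to 7, that is 10 + 9 + 8 + 7 + 6 + 5 + 4 = 49 of the 98 schedules.

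These are counts of permitted schedules, not probabilities; sites will not use all of them equally often.

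**Does anything else cover the remaining days?**

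| Provision | What it covers | Does it elicit new events through day 14 in all these completers? |
|---|---|---|
| Section 5.5, unresolved events | 30 days, only if an event is unresolved at exit | No |
| Section 5.5, gastrointestinal events of interest | At least 6 months, only if such an event occurred | No |
| Appendix 6, note 3 | Review of events already ongoing | No |
| Appendix 2, post-challenge instruction 6 | A follow-up appointment as per protocol | Appendix 5 lists none after the exit challenge |
| Section 8.8 | Events found at visits, through site contact or in the diary | Spontaneous report only after the last call |
| Section 8.8.2.1 | Related serious events reported after the period | Does not elicit events within the period |

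**The case against.** The strongest reply is that a reporting period is not a visit schedule. Under Section 8.8, an event that a parent telephones in on day 10 is collected, and Appendix 2 has the site give contact and after-hours details before release. That is correct: collection remains open. What is missing is active questioning, which early discontinuers receive. The two are not equivalent for non-serious events.

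Four stronger readings are tempting, and the documents do not support them.

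- **No contact at all after the last call.** Completers with events unresolved at exit or gastrointestinal events of interest do have follow-up. The gap is in scheduled contact for the others, and in questioning about new events.
- **Twelve of 14 days lost in every completer.** This requires the last dose to fall on the day before the baked egg challenge, which is inferred from the withholding instruction and not stated. Reading B gives a different range. Section 5.4 also lets blinded treatment continue where the follow-on study is not yet available. Any dosing after the exit challenges would move the last dose later and lengthen the gap.
- **A bias between arms because more AR201 subjects drop out.** The protocol projects no dropout by arm. Its only by-arm figures come from the cited multicenter egg immunotherapy trial (Section 1.1): 5 of 40 on immunotherapy (12.5%) and 2 of 15 on placebo (13.3%) withdrew before maintenance. They show no difference.
- **Challenge reactions going unseen.** Both exit challenges have on-site observation and a next-day call, and the protocol's own anaphylaxis criteria describe onset within minutes to hours. The uncovered days are not when such reactions would be expected.

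Figure 4, which depicts the reporting period, is not available in the text reviewed. Its footnote mentions only the same safety follow-up.

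**Conclusion.** The inconsistency stands. Sections 8.8.1 and 10.6 promise 14 days to all subjects not receiving AR201 in the follow-on study, and Appendix 5 schedules the corresponding assessment only for early discontinuers. Neither reading of the last-dose date guarantees the window for the other group. The shortfall is 10 to 12 days if dosing continues between challenges, the more natural reading of note 12. If dosing ends before the first challenge day, about half of the permitted schedules fall short.

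Post-treatment ascertainment therefore depends on completion status. This would distort the comparison of arms only if completion or follow-on entry differed by arm, which the protocol does not show. The number of completers who will not roll over is not given either, so neither the direction nor the size of any effect can be stated. The point is worth correcting because the stated period and the schedule disagree and the remedy is small; no bias has been demonstrated.

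**What to change.** Add to Appendix 5 a telephone review of adverse events and concomitant medications about 14 days (±3) after the last dose, for completers who do not enter the follow-on study. This matches the timing and visit window already used for early discontinuation. State in Section 8.8.1 that this contact closes the adverse event period for these subjects, and make clear from which recorded last-dose date the 14 days are counted.

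The cost is one call per such completer and one line in the schedule. The sponsor could instead shorten the stated window to what is actually assessed. That would remove the contradiction but leave the two disposition groups followed for different lengths of time.
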